10.5 Final Analysis Plan

10.5.1 General Considerations

The SAP, which includes more technical and detailed elaboration of the principal features stated in the protocol, will be prepared separately and finalized before the interim analysis.

Safety will be assessed by estimating the occurrence of Grade 2 or higher treatment-emergent AEs in the IV bacteriophage therapies compared to placebo through Day 30 ± 7 days.

Microbiological activity will be assessed by estimating changes in $\log_{10} P. aeruginosa$ CFU/mL (total and each morphology) in sputum cultures from baseline through Day 30 ± 7 days.

The benefit to risk profile will be assessed by comparing the DOOR of IV bacteriophage arms and placebo arm through Day $8 + 3$ days. The DOOR will be analyzed by estimating the DOOR probability (Section 10.5.5), (i.e., the probability of a randomly selected subject having a better DOOR if assigned to receive an IV bacteriophage therapy compared to placebo).

All statistical calculations will be performed using up-to-date versions of SAS version 9.4 or higher (SAS Institute Inc., Cary, NC, USA) or language and environment for statistical computing 3.6.1 or higher (R Foundation for Statistical Computing, Vienna, Austria), unless otherwise specified. All PK analyses will be performed using NONMEM version 7.3 or higher (ICON Development Solutions, [name]). For continuous variables, summary statistics will include sample size, mean, SD, median, quartiles, minimum, and maximum values. Frequencies and percentages will be calculated for categorical variables. All reported confidence intervals will be two-sided 95%. Graphical displays will be produced.

10.5.2 Analysis Sets

Four analysis sets will be considered in the statistical analysis of the study:

1. *Screened Set*: The screened set will consist of all subjects who undergo the Screening Visit and receive a patient identification (PID) number.
2. *Intent-to-treat/Randomized Set*: The intent-to-treat (ITT) set will consist of all randomized subjects regardless of whether or not they received study product or placebo.
3. *Safety Set*: The safety set will consist of all randomized subjects who received at least one dose of study product or placebo. Subjects will be analyzed based on the treatment received.
4. *Pharmacokinetics Set*: The PK set will consist of all randomized subjects who contributed at least two of each a sputum and a blood sample.

On the basis of the ITT principle, all of the primary endpoints will be analyzed on the ITT set.

10.5.3 Subject Disposition

The number of subjects in two of the study sets (ITT and Safety) will be summarized by groups; the screened set will only be summarized by study center.

Screen failures (i.e., subjects screened but not randomized) and the associated reasons for failure will be tabulated overall. The number and percentage of subjects who complete the treatment period (including Day 30 ± 7 days) and of subjects who prematurely discontinue during the same period will be presented for each group and pooled across groups for the ITT set. The reasons for premature discontinuation as recorded on the termination pages of the eCRF will be summarized (number and percentage) by treatment groups for ITT set.

10.5.4 Demographics and Other Baseline Characteristics

Demographic variables and other baseline characteristics will be summarized by treatment arm for the Safety and ITT sets.

Prior medication is defined as any medication taken before the date of study product or placebo. Concomitant medication is defined as any medication started on or after the date of study product or placebo dose.

Concomitant medication use will be summarized by the number and proportion of subjects in each arm receiving each medication within each therapeutic class for the safety set. If a subject took a specific medication multiple times or took multiple medications within a specific therapeutic class, that subject would be counted only once for the coded drug name or therapeutic class.

10.5.5 Analysis of Primary Endpoints

Grade 2 or higher treatment-emergent AEs will be summarized descriptively. The type of AE, number of events (n) and number (%) of subjects with events in each arm will be tabulated. The type of AE, number of AEs and the number (%) of subjects with events will be presented by system organ class (SOC), HLT, and preferred term. Subjects are counted once in each SOC, HLT, and preferred term. The difference in proportion of the number (%) of subjects with events between IV bacteriophage and placebo arms will be calculated with the corresponding exact 95% confidence interval.

Changes in \log_{10} *P. aeruginosa* CFU/mL (total and each morphology) in quantitative sputum cultures from administration of IV bacteriophages through Day 30 (\pm 7 days), Visit 7, will be summarized descriptively. Descriptive statistics will be presented by arms. The difference in mean change between IV bacteriophage and placebo arms will be estimated with the corresponding 95% confidence interval (\log_{10} -transformed and original scales). Area Under Curve (AUC) calculated using the trapezoidal rule will be used to summarize \log_{10} *P. aeruginosa* CFU/mL over the time. The difference in AUC between IV bacteriophage and placebo arms will be calculated with the corresponding 95% confidence interval.

The DOOR will be summarized by estimating the DOOR probability, using the equation

$$\text{DOOR probability} = \Pr[\text{DOOR}_{\text{IV}} > \text{DOOR}_{\text{P}}] + \frac{1}{2} \Pr[\text{DOOR}_{\text{IV}} = \text{DOOR}_{\text{P}}],$$

where DOOR_{IV} and DOOR_{P} are the DOOR for bacteriophage and placebo arms, respectively, and $\Pr[\text{DOOR}_{\text{IV}} > \text{DOOR}_{\text{P}}]$ is the proportion of a DOOR from IV bacteriophage dose exceeding a DOOR from placebo and $\Pr[\text{DOOR}_{\text{IV}} = \text{DOOR}_{\text{P}}]$ is the proportion of two DOOR outcomes being same. The corresponding 95% confidence interval will be calculated.

In addition, the DOOR will be analyzed as follows: DOOR distribution by arms, cumulative difference (point estimate and confidence band) in DOOR categories for bacteriophage vs. placebo, point estimate and confidence interval of difference in mean partial credit vs. placebo, and DOOR distribution for bacteriophage vs. placebo arm.

Each of the components of the DOOR will be compared between the IV bacteriophage and placebo arms: presence/absence of SAE and reduction in *P. aeruginosa* CFU/mL ($> 2 \log_{10}$, 1-2 \log_{10} reduction, $< 1 \log_{10}$ reduction).

All analyses are summarized in the **Table 3** below.

Table 3: Summary of Analysis of Primary Endpoints

Outcome/Variable	Summary Measures	Analysis of Methods	Analysis Set
1) Grade 2 or higher treatment-emergent AEs	
 The number of events The number of subjects with events Evaluated until Day 30 	
 Descriptive statistics (frequency and percentage) in each arm Difference in bacteriophage vs. placebo arm and the corresponding 95% confidence interval 	ITT
2) $\log_{10} P. aeruginosa$ CFU/mL	
 Mean change from baseline Evaluated until Day 30 	
 Descriptive statistics (the number of subjects, mean, SD, quartiles, minimum, median, and maximum) Confidence interval for mean change from baseline in each arm Difference in mean change from bacteriophage vs. placebo arm and its corresponding 95% confidence interval (\log_{10}-transformed and original scales) Plot median (Q1,Q3) over time by arm AUC over times Difference in AUC of bacteriophage vs. placebo and its corresponding 95% confidence interval. 	ITT
3) DOOR	
 DOOR Probability 	
 95% confidence interval for DOOR Probability of bacteriophage vs. placebo 	ITT

Outcome/Variable	Summary Measures	Analysis of Methods	Analysis Set
	
• DOOR Categories distribution• Evaluated until Day 8	
• Descriptive statistics (frequency and percentage) in each arm• Cumulative difference in DOOR categories for bacteriophage vs. placebo (point estimate and confidence band)• Point estimate and confidence interval of difference in mean partial credit of bacteriophage vs. placebo arm• DOOR distribution of bacteriophage vs. placebo arm	

10.5.6 Subgroup and Adjusted Analyses for Primary Endpoints

As an explanatory analysis, subgroup analyses of the primary outcomes may be conducted to explore whether estimated treatment effects vary significantly between subcategories of trial subjects, including, but not limited to, bacteriophage susceptibility and presence of co-infection with other organisms recovered on sputum cultures collected during the study period. In addition, the primary endpoints will adjust for pre-randomization variables, which might reasonably be expected to be predictive of favorable outcomes.

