3 STUDY DESIGN, OBJECTIVES AND ENDPOINTS OR OUTCOME MEASURES

3.1 Study Design Description

This is a Phase 1b/2, multi-center, randomized, placebo-controlled, double-blind study of a single dose of IV bacteriophage in approximately 72 clinically stable adult CF subjects colonized with *P. aeruginosa* in expectorated sputum. The primary study outcomes include safety and microbiological activity of IV bacteriophage therapy.

As part of screening, an expectorated sputum sample will be obtained from each subject and tested for the presence of *P. aeruginosa*. If *P. aeruginosa* is isolated from the sputum and all eligibility criteria are met, the subject will be eligible for the study. If *P. aeruginosa* is not isolated, the subject will be considered a screen failure. Screening for susceptibility of *P. aeruginosa* to the 4-component bacteriophage mixture will not occur prior to administration of study treatment.

Stage 1 (Unblinded Safety Assessment/Dose-Escalation in Sentinel Subjects): Following screening, eligible subjects will be assigned into one of the three IV bacteriophage dosing regimens (arms). A total of 6 sentinel subjects will be enrolled in Stage 1 of the study. The arms will be sequentially enrolled with dose escalation by one \log_{10} starting at 4×10^7 PFU. In each dosing arm, two subjects will be enrolled to serve as sentinels. Each sentinel subject will receive a single dose of IV bacteriophage therapy, followed by a 30 ± 7 days observation period. Refer to Section 8.2.3.1 for details regarding dosing in sentinel subjects.

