- ***P. aeruginosa* colony counts** will be performed by the central lab using quantitative bacterial cultures on sputum specimens collected from the time of bacteriophage administration through Day 30 ± 7 days. Quantities of sputum (10 mg) will be measured precisely and added to 1 mL Sputolysin mucolytic agent to liquefy the sample. The liquefied sample will be diluted sequentially and plated onto MacConkey agar and Sheep's Blood Agar Plates using a 1 μ L loop for each replicate. Colonies will be counted on the highest dilution in which individual colonies can be enumerated and colony counts adjusted appropriately based on the dilution factor and the mass of the sample to determine the true concentration of *P. aeruginosa*. Colonies representing different morphotypes will be definitively identified using MALDI-TOF to ensure that each enumerated colony type represents *P. aeruginosa*. Refer to the MOP for additional details.
- ***P. aeruginosa* susceptibility to bacteriophages** may be performed by the central lab on *P. aeruginosa* isolates in sputum cultures, depending on sample availability.

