## 4.6. Exploratory Endpoint Variables

There will be four exploratory objectives: (1) characterize the serum and sputum PK profiles of a single dose of IV bacteriophage therapy in clinically stable CF subjects with *P. aeruginosa* in expectorated sputum, (2) change in lung function from the administration of a single dose of IV bacteriophage therapy through Day  $30 \pm 7$ , (3) characterize geographically diverse *P. aeruginosa* isolates susceptibility to bacteriophages, and (4) describe subjects' QoL before and after receiving bacteriophages. The SAP for the first exploratory objective, related to serum and sputum PK, will be provided in a separate document.

Change in lung function will be measured using FEV1. Spirometry will be performed at screening, baseline, and at follow-up visits occurring on Days 2, 5, 12, and 30.

Phage susceptibility testing (PST) will occur using a plaque assay and the liquid assay. These assays describe the proportion of *P. aeruginosa* isolates that are susceptible to each phage and to the phage cocktail. Both the plaque assay and liquid assay will be evaluated every time sputum is obtained (see schedule of study

procedures in [Table 1](#)). An isolate will be considered susceptible to phage if both the plaque assay and the liquid assay indicate susceptibility.

The CFQ-R (<https://cfqr-app.netlify.app/#/questionnaire>) is a self-administered QoL questionnaire designed to measure the impact that CF has on overall health, daily life, and perceived well-being and symptoms. The CFQ-R contains 50 items and will be administered at in-person and virtual study visits for Stage 2 subjects. The CFRSD (<https://depts.washington.edu/seaqol/CFRSD-CRISS>) is a subject reported outcome measure that is used to evaluate the effect of treatment on respiratory infection symptom severity in patients with CF and chronic respiratory infection. Quality of Life will be measured using the CFQ-R and the CFRSD. The CFQ-R will be administered at baseline and at the final follow-up visit (Day  $30 \pm 7$ ). The CFRSD will be administered at baseline and at follow-up visits occurring on Day 2, 5, 8, and 30.

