### 8.2.4. Subgroup Analyses

A subgroup analysis of the primary endpoints will be conducted to explore whether estimated treatment effects vary significantly between subcategories of trial subjects, including bacteriophage susceptibility and presence of co-infection with other organisms recovered on sputum cultures. Analysis of the difference in

mean change between IV bacteriophage and placebo arms and the  $\log_{10}$ -transformed difference in mean change, along with the corresponding 95% CIs, will be presented by subgroup in [Table 22](#). A forest plot of the differences in *P. aeruginosa* colony counts is presented by subgroup in [Figure 8](#) and a forest plot of differences in the  $\log_{10}$  *P. aeruginosa* colony counts is presented by subgroup in [Figure 9](#). Analysis of the primary DOOR endpoint at Day 8 will be presented by subgroup in [Table 29](#) and a contingency table of DOOR by subgroup, treatment group, and time point will be presented in [Table 30](#). A forest plot of DOOR probability in subgroups will be presented in [Figure 11](#).

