Maximum	Selected Dose (N=X)	x	xx.x	xx.x	xx	xx, xx	xx, xx	xx, xx	xx.x	xx.x	xx	xx, xx	xx, xx	x.xx, x.xx	
	Placebo (N=X)	x	xx.x	xx.x	xx	xx, xx	xx, xx	xx, xx	xx.x	xx.x	xx	xx, xx	xx, xx	x.xx, x.xx	
[Repeat for all morphologies]															

Notes: N=Number of subjects in the ITT population in Stage 2a and 2b.

n=Number of subjects in the ITT population in Stage 2a and 2b with non-missing colony counts at the time point of interest. For the change from baseline, n represents the number of subjects in the ITT population with non-missing values at baseline and at the time point being assessed.

SD=Standard Deviation

Baseline is defined as the last measurement taken prior to dosing on Study Day 1.

aQ1 and Q3 represent the 25th and 75th percentiles, respectivelyb95%CI is calculated from a t-distribution.

**Table 37: Proportion of *P. aeruginosa* Isolates Susceptible to Individual Bacteriophages – ITT Population, Stage 2a and 2b**

[Implementation note: ‘Selected Dose’ will be replaced with the dose chosen by the interim analysis. If multiple timepoints are collected, then this table will be stratified by timepoint with an additional ‘All Timepoints’ category.]

P. aeruginosa Isolate	Selected IV Bacteriophage Dose				Placebo				Difference 95% CI b
	N	n	%	95% CI a	N	n	%	95% CI a	
[Bacteriophage 1]									
[Isolate 1]	x	x	x	(x.x, x.x)	x	x	x	(x.x, x.x)	xx (x.x, x.x)
[Isolate 2]	x	x	x	(x.x, x.x)	x	x	x	(x.x, x.x)	xx (x.x, x.x)
[Isolate 3]	x	x	x	(x.x, x.x)	x	x	x	(x.x, x.x)	xx (x.x, x.x)
[Isolate 4]	x	x	x	(x.x, x.x)	x	x	x	(x.x, x.x)	xx (x.x, x.x)
[Repeat for each bacteriophage]									

Notes: *P. aeruginosa* isolate will be identified by individual morphotype ID.

N=Number of subjects in the ITT population in Stage 2a and 2b with non-missing values for isolate susceptibility.

n=Number of subjects with isolates susceptible to the corresponding bacteriophage.

a95% CI for proportions calculated using the Wilson method.

b95% CI for the difference in proportions, IV bacteriophage relative to placebo, calculated using the Miettinen–Nurminen method.

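### The co-infection and susceptibility subgroups are not tied to pre-dose sputum, so membership can depend on treatment and the subgroup contrasts may not be randomised comparisons.

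*Protocol*

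**What the plan says.** Protocol 10.5.6 introduces the subgroups as optional: "As an explanatory analysis, subgroup analyses of the primary outcomes may be conducted". It names two, bacteriophage susceptibility and "presence of co-infection with other organisms recovered on sputum cultures collected during the study period". The next sentence, on covariate adjustment, does carry a timing limit: "the primary endpoints will adjust for pre-randomization variables". No such limit is placed on the subgroups.

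The SAP makes the analysis firm rather than optional. Section 8.2.4 covers subcategories "including bacteriophage susceptibility and presence of co-infection with other organisms recovered on sputum cultures". It omits the reference to the study period but names no other time point. Section 6.4 names susceptibility as the only pre-specified subgroup and is also silent on timing.

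On testing, Protocol 3.1 says that screening for susceptibility to the "4-component bacteriophage mixture will not occur prior to administration of study treatment". Protocol 7.2.2 makes testing optional, on "isolates in sputum cultures, depending on sample availability". SAP 4.6 is broader: "Both the plaque assay and liquid assay will be evaluated every time sputum is obtained". The note to SAP Table 37 anticipates repeated results: "If multiple timepoints are collected, then this table will be stratified by timepoint with an additional" category for all time points.

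The subgroup displays (SAP Tables 22, 29 and 30; Tables 7-8 and 18-21 of the SAP addendum on undetectable results) use one yes/no label per subject.

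**The concern.** A subgroup contrast keeps the protection of randomisation only if membership is fixed before treatment can act on it. Here the sputum that supplies the post-dose colony count can also supply the subgroup label.

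For susceptibility, two mechanisms are plausible. Phage exposure may select resistant isolates, and Protocol 2.1 lists the kinetics of phage resistance in clinical use as a knowledge gap. A subject whose *P. aeruginosa* becomes undetectable leaves no isolate to test; the addendum reports 2 of 32 Stage 2a subjects undetectable at every post-baseline time point. For co-infection, other organisms might be recovered more readily once *P. aeruginosa* falls, but the documents offer no evidence on this.

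What is at stake is interpretation. Subjects enrol without regard to susceptibility, so the susceptible stratum is where a reader will look for evidence of activity. The DOOR subgroup tables (SAP Table 29; addendum Tables 18 and 19) also carry a footnote under which superiority is concluded when the lower confidence limit exceeds 0.5.

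**Working it through.** The plan states no figure for the subgroup analyses, so there is none to reproduce. The check is of the text, followed by illustrations whose rates are all assumed.

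**1. Which samples fall in the window.** Protocol 7.2.1 and Appendix A schedule Stage 2 sputum at screening, Day 1 pre-infusion, Day 1 post-infusion, and Days 2, 5, 8 and 30. That is seven samples, five of them post-dose.

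**2. Is there a pre-dose restriction elsewhere?** SAP 3.3.2 defines a baseline value as the last one before dosing, but nothing says subgroup membership uses it. SAP 4.6 has an isolate-level rule (both assays must show susceptibility) but no subject-level rule. SAP Listings 10 and 13 hold other organisms and susceptibility by planned time point; no text says which visit or morphotype decides the single label.

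**3. Direction of bias, susceptibility and DOOR.** Assume ranks 1/2/3 of 0.32/0.30/0.38 in truly susceptible phage subjects and 0.05/0.15/0.80 on placebo, with no rank 4.

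DOOR = P(phage better) + ½P(tie) = (0.32×0.95 + 0.30×0.80) + ½(0.32×0.05 + 0.30×0.15 + 0.38×0.80) = 0.544 + 0.1825 = 0.727.

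Now apply a post-dose label. *Conversion*: in the phage arm, 30% of rank 3 and 10% of ranks 1-2 become non-susceptible. The remaining weights are 0.288, 0.270 and 0.266 (sum 0.824). *Loss*: a share of rank 1 in both arms has no post-dose isolate. Rescale each arm to 1 and reapply the formula:

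| Labelling | Phage 1/2/3 | Placebo 1/2/3 | DOOR |
|---|---|---|---|
| Pre-dose | 0.320/0.300/0.380 | 0.050/0.150/0.800 | 0.727 |
| Conversion only | 0.350/0.328/0.323 | 0.050/0.150/0.800 | 0.757 |
| Conversion, 25% loss | 0.287/0.359/0.354 | 0.038/0.152/0.810 | 0.743 |
| Conversion, 50% loss | 0.212/0.397/0.391 | 0.026/0.154/0.821 | 0.726 |
| Conversion, 75% loss | 0.118/0.444/0.438 | 0.013/0.156/0.831 | 0.703 |
| 50% loss only | 0.190/0.357/0.452 | 0.026/0.154/0.821 | 0.694 |

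The sign depends on the balance of the two mechanisms, which the documents do not give.

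**4. Susceptibility and log10 counts, no phage effect at all.** Suppose half the subjects have poor prognosis, worse by d log10, and phage converts a share r of the poor-prognosis susceptible subjects. Bias in the susceptible stratum (phage minus placebo change) is d × [(1−r)/(2−r) − ½].

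- r = 0.25, d = 1: 0.75/1.75 − 0.5 = −0.07.
- r = 0.75, d = 1.5: 1.5 × (0.25/1.25 − 0.5) = −0.45.

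Simulating 8,000 trials (25 per arm, 60% susceptible, SD 1, Welch test), two-sided rejection in that stratum was 5.4%, 6.3%, 8.0% and 14.1% for (r, d) = (0.25, 1), (0.5, 1), (0.5, 1.5) and (0.75, 1.5). With a pre-dose label it was 4.7% to 5.2%. This example has conversion only, so it shows one direction.

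**5. Co-infection.** Assume a uniform effect of −1.0 log10, 30% baseline prevalence, and 20% to 40% added recovery when *P. aeruginosa* falls by more than 1 log10. Prevalence becomes 37% to 44% on phage against 32% to 37% on placebo. The effect reads −1.02 to −1.06 in co-infected subjects and −0.90 to −0.97 in the rest. The pre-dose label returns about −1.0 in both.

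**6. Against sampling noise.** With 60% of 25 susceptible, there are 15 per arm. The tie-free standard error of the DOOR probability is √[31/(12×15×15)] = 0.107; ties reduce it. The shifts in step 3 run from 0.694 − 0.727 = −0.033 to 0.757 − 0.727 = +0.030, or about 0.3 standard errors.

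**The case against.** The strongest reply is that nothing obliges the statistician to use a post-dose label. The study period also contains the screening and pre-infusion samples, SAP 8.2.4 omits the study-period phrase, and SAP 3.3.2 supplies a pre-dose baseline. Repeated susceptibility testing serves a separate exploratory endpoint, the proportion of isolates susceptible, and so does not show that a post-dose label is planned. The analyses are exploratory, no formal hypothesis testing is planned, and any distortion may be small beside the noise in strata of this size.

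Much of this stands. The two subgroups are on different footing: for co-infection the protocol's own wording admits post-dose cultures, whereas for susceptibility the point rests on silence combined with repeated testing. What does not stand is that silence is harmless. The rule would be chosen when post-dose results already exist, and the protocol shows awareness of the principle by limiting covariates to pre-randomisation variables.

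A reader might infer that a post-dose label would inflate the effect in susceptible subjects. The documents do not support that: losing cleared responders acts in the opposite direction, as step 3 of the working shows.

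**Conclusion.** The definitional gap is real and worth closing. Membership of both subgroups *can* depend on treatment, so the subgroup contrasts *may* not be randomised comparisons. The documents permit a post-dose label; they do not require one.

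Neither the direction nor the size of any bias can be established from the documents. Every conversion, loss, prognosis and recovery rate above is an assumption, as are the rank distributions and the SD. The illustrations show only that the DOOR shift can have either sign, and that in these examples it is modest relative to sampling error.

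A reader might also infer that the trial's main results are compromised. They are not: the ITT primary contrasts do not use these labels. The practical risk is over-reading a susceptible-stratum result in tables that carry a superiority footnote.

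**What to change.** In Protocol 10.5.6 and SAP 6.4 and 8.2.4:

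- Define both subgroups from pre-dose sputum only: the Day 1 pre-infusion sample, with the screening sample as fallback if that yields no isolate.
- State one rule for subjects with several morphotypes of differing susceptibility.
- Place subjects with no tested pre-dose isolate in an unknown group.
- Keep post-dose susceptibility as an outcome by arm and time point, as Table 37 already allows.

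Two repairs belong with this. SAP 6.4 (susceptibility the only pre-specified subgroup) should be reconciled with 8.2.4 and the tables, which also include co-infection. The notes to SAP Table 22 and addendum Tables 7 and 8 list the susceptible-yes stratum twice and omit susceptible-no.

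The cost is wording; no new visit or sample is needed. Inclusion criterion 5 requires *P. aeruginosa* from screening sputum, so a fallback source should exist, but the documents do not say whether that isolate is kept, and this needs confirming. The downside is that some subjects will be unknown: testing depends on sample availability, and 3 of 32 Stage 2a subjects had undetectable baseline counts.
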